**Part 3 – EOT and follow-up period (all patients)**

VISIT NO.	██████ ██████ ██████	███ ██████ ██████	██████████ ██████ ██████████ ██████████	██████	███ ██████
Study Day (± 3d)	██████	██████	██████	██████████	██████████
Study Week	██████	██████	██████	██████	██████
Informed consent					
In- / exclusion criteria 					
MDS/AML related medical history					
Concomitant MDS/AML specific medication	x	x	x	x	
Physical examination, vitals	x	x	x	x	
BMI	x	x	x	x	
Pregnancy test 	x	x	x	x	
Toxicity/AE assessment	x	x	x	x	
Quality of life (QoL, EORTC QLQ-C30)	x	x	x		
Information on current state of condition / survival status	x	x	x	x	x
Central assessments / correlative analyses (EU: Leipzig, AUS: QIMRB, Brisbane)					
Bone marrow aspiration (5 mL sodium heparinized in separate tubes for central assessments)		x 			
Peripheral blood sampling for central assessments (10 mL sodium heparinized blood in separate tubes for central assessments)		x 			
Genetic profiling (NGS) at central laboratories		x			
MRD analyses at central laboratories					
Telomere length & telomerase profiling at central laboratories		x			
Study-specific biomaterial collection		x			
Local assessments					
Serum chemistry (local)	x	x	x		
Automated CBC (local)	x	x	x		

 FU2/EOS can be carried out on the telephone

 To be carried out once the results of the response assessment from █████ are available and at the latest 14 days after the date of decision of treatment discontinuation

 Responders after the assessment at █████ will be treated further until loss of response/disease progression. In the case of safety issues, loss of response or disease progression, patients will undergo the EOT visit within 14 days from the date of decision of treatment discontinuation.

 BM and PB sample collection should only be performed at EOT visit if > 90 days from prior BM procedure

## 2.7 Randomization and Stratification

This is an open-label, single-arm trial. Therefore, randomization techniques are not applicable.

Due to the transient improvement seen in WBC and peripheral blasts in patients early in treatment, the study will continue in an exploratory approach with a change in dose frequency. Therefore, two cohorts will be defined by treatment regimen:

- Cohort 1: Subjects screened before IA receiving dosage once in a ■■■ day cycle for at least ■ cycles
- Cohort 2: Subjects screened after IA receiving dosage twice in a ■■■ day cycle (once every ■■ days) for at least ■ cycles

## 2.8 Blinding

This is an open-label, single-arm trial. Therefore, blinding techniques are not applicable.

## 2.9 Planned Interim or Sequential Analysis

Simon's two stage design is used in this study, with an IA at the first stage following assessment of ■■ evaluable patients. If the number of responses is less than or equal to ■ out of ■■ patients in the first stage, then the trial will be stopped for futility. The final analysis will be conducted based on the total evaluable ■■ patients if there are ■ or more responses in the first stage.

Further details regarding the planned IA are provided in Section 5.

## 2.10 Handling of Changes to Study Protocol

In case of prospective changes to the planned analyses that represent a substantial deviation from the protocol, these will be added to and explained in the clinical study protocol in a substantial protocol amendment. Any prospective changes that do not fulfil the requirements for a major protocol amendment should be included in an update to the SAP that should be finalized prior to database lock. All deviations and/or alterations from the envisaged analysis that occurred after database lock and their reasons will be described and discussed in detail the clinical study report (CSR).

### 3. Technical Aspects

#### 3.1 General Aspects

All programs will be written using SAS® Version 9.4 or higher. There will be an individual SAS® program written for each table, figure, and listing, where tables or figures generated for different subgroups do not necessarily require separate programs. Each analysis program will be validated by a second qualified SAS® programmer to ensure a correct output and a correct presentation of the data. The validation process is documented in the validation sheet (GCPS\_DMF\_033 A-C), which also prespecifies criteria for risk categorization of programs and the corresponding validation actions.

All outputs will be generated in English language as RTF documents with DIN A4 format and will be saved as write-protected PDF documents with tables of contents preceding the content of the file. There will be one RTF/PDF document for tables, one for figures and one for listings. Courier New is used as font. The font size should be consistent within each document and reasonable, i.e., there should be as much required information as possible on one page, but the text should still be easy to read.

In headings, titles, and listings only the first word will be capitalised. If missing data are displayed in a subject listing, they are represented as blank field. Listings will be sorted by subject number unless specified otherwise. A list of all planned tables, figures and listings can be found at the end of this SAP and the layout of these tables and listings is provided in the documents IMpress\_YYYYMMDD\_mockTables\_v1.0 and IMpress\_YYYYMMDD\_mockListings\_v1.0

#### 3.2 Data Conversion

Final study data will be converted into the Study Data Tabulation Model (SDTM) defined by the Clinical Data Interchange Standards Consortium (CDISC). EDC data as well as external data (e.g., laboratory data and protocol deviations) will be mapped to SDTM according to SDTM Implementation Guide version 3.3 and NCI Controlled Terminology in effect at the time the conversion is started will be followed.

The final SDTM domains will be used to generate analysis datasets according to the Analysis Dataset Model (ADaM) defined by CDISC. The data from the SDTM domains will be mapped to ADaM datasets according to the ADaM Implementation Guide version 1.2 and NCI Controlled Terminology in effect at the time the conversion is started will be followed.

The ADaM datasets will support each statistical analysis described in this SAP. Deviations have to be agreed with the Sponsor and at least described in the Analysis Data Reviewer's Guide.

## 4. Analysis Sets and Subgroups

### 4.1 Analysis Sets

#### 4.1.1 Full Analysis Set (FAS)

The Full Analysis Set (FAS) consists of all patients who received at least one dose of study drug and fulfilled the inclusion criteria. The FAS is the primary dataset for analysis.

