2.3 Study endpoints

2.3.1 Primary endpoint

The primary endpoint of the study is defined as overall hematological response rate as assessed in [REDACTED] of treatment with imetelstat.

All patients with one of the following responses assessed by samples and procedures taken/carried out at [REDACTED] are defined as responders (assessed through the combined response criteria for MDS and AML used in this trial (see Appendix III a), section 16.3):

[1] CR, CRi, PR as defined in Appendix III a)

[2] Hematologic improvement (for one or several lines) as defined in Appendix III a)

Response rate is calculated as follows: number of responders divided by the number of all patients of the analysis set. Patients for whom the overall hematologic response cannot be determined will be considered as treatment failures.

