6.3 Inclusion criteria

Subjects must fulfill all of the following criteria before inclusion in the study:

- 1 Signed written informed consent
- 2 Male and female ≥ 18 years at the first screening
- 3 Must be able to adhere to the study visit schedule and other protocol requirements
- 4 Initial diagnosis of AML or MDS according to WHO 2016 classification
- 5 At least one cytopenia (ANC $< \blacksquare/\mu\text{L}$ or platelet count $< \blacksquare/\mu\text{L}$ or hemoglobin $< \blacksquare \text{ g/dL}$)
- 6
 - a. Failure to achieve complete or partial response or hematological improvement observed after at least six azacitidine monotherapy or four decitabine monotherapy based 4-week treatment cycles administered during the past two years
OR
 - b. Failure to achieve complete or partial response or hematological improvement observed after at least two 4-week treatment cycles with azacitidine plus venetoclax or with decitabine plus venetoclax during the past two years

- OR
- c. Relapse after initial complete or partial response or hematological improvement observed after at least six (azacitidine) or four (decitabine) based 4-week treatment cycles administered during the past two years
- OR
- d. Relapse after initial complete or partial response or hematological improvement observed after at least two 4-week treatment cycles with azacitidine plus venetoclax or with decitabine plus venetoclax during the past two years
- OR
- e. Intolerance to treatment with HMA-based therapy during the past two years
- 7 Not eligible for allogeneic stem cell transplantation
- 8 $\geq 5\%$ bone marrow blasts at screening
- 9 Off all other treatments for AML/MDS for at least 14 days; G-CSF and erythropoietin are allowed before and during the study as clinically indicated
- 10 ECOG performance status of 0-2
- 11 Biochemical laboratory test values must be within the following limits:
[REDACTED]
[REDACTED]
[REDACTED]
[REDACTED]
[REDACTED]
- 12 Availability of blood counts and transfusion events for previous 16 weeks
- 13 Women of childbearing potential and practicing a highly effective method of birth control according to the Clinical Trial Facilitation Coordination Group Recommendation (Version 1.1, 2020):
- combined (estrogen and progestogen containing) hormonal contraception associated with inhibition of ovulation:
 - o oral
 - o intravaginal
 - o transdermal
 - progestogen-only hormonal contraception associated with inhibition of ovulation:
 - o oral
 - o injectable

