10.2 Analysis sets

10.2.1 Full Analysis Set (FAS)

The Full Analysis Set (FAS) consists of all patients who received at least one dose of study drug and fulfilled the inclusion criteria. The FAS is the primary dataset for analysis.

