#### 4.1.3 Safety Evaluation Set (SES)

Safety summaries will be based on the Safety Evaluation Set, which will consist of all patients who received at least one dose of study drug.

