## 7.3 Data Review

Data are checked and cleaned during the course of the study. Protocol deviations such as time window deviations are identified during monitoring and by data management checks. The statistical programmer will collect the protocol deviations. Additional protocol deviations might be identified and added during this data review.

Classification of protocol deviations into critical and non-critical will be discussed between Sponsor and statistician prior to database lock, with the final decision being made by the Sponsor. A critical protocol deviation is defined as protocol deviation which might influence the outcome of the primary analysis (e.g., a violation of eligibility criteria detected after enrolment). The free choice of subjects to terminate their study participation prematurely is described in the study protocol and thus not regarded as protocol deviation but as reason for exclusion from the per protocol set. The following list of criteria can be used to identify critical protocol deviations and is not meant to be exhaustive:

- Violation against eligibility criteria
- Deviation from visit window of primary endpoint visits.
- Assessment of primary endpoint not performed
- Use of disallowed concomitant medication

For further details it is referred to the Data Review Meeting Plan (DRM).

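### The primary efficacy set drops treated patients found to have failed an inclusion criterion, keeps those who broke an exclusion criterion, and is not backed by an all-treated response rate

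*SAP*

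**What the plan says.** - **Primary set.** SAP 4.1.1 states that the FAS "consists of all patients who received at least one dose of study drug and fulfilled the inclusion criteria". Protocol 10.2.1 has the same rule: patients who "received at least one dose of study drug and fulfilled the inclusion criteria. The FAS is the primary dataset for analysis". Neither mentions the exclusion criteria.
- **Safety set.** SAP 4.1.3 defines the Safety Evaluation Set (SES) as "all patients who received at least one dose of study drug". It serves safety only.
- **Response rate.** Protocol 2.3.1 defines it as the "number of responders divided by the number of all patients of the analysis set" and adds: "Patients for whom the overall hematologic response cannot be determined will be considered as treatment failures". SAP 7.7.4 repeats the failure rule.
- **Sets used.** Response is analysed on the FAS and repeated on the PPS (Protocol 10.8.1); SAP 8.3 repeats it only if the sets differ by more than 10% in size. The PPS is a subset of the FAS. Secondary efficacy endpoints use the FAS (Protocol 10.8.2, SAP 8.4).
- **Late violations.** SAP 7.3 gives "a violation of eligibility criteria detected after enrolment" as its example of a critical deviation. Deviations are classified as critical or non-critical before database lock, "with the final decision being made by the Sponsor".
- **Setting.** The trial is open-label and single-arm (SAP 2.8), response is assessed locally by the investigator (Protocol 8.2.4), and the primary outcome is analysed after the last patient has finished the study (SAP 2.1.6).

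**The concern.** Protocol 8.1.2 requires eligibility to be checked at enrolment, before treatment starts. The inclusion condition in the FAS therefore acts mainly on violations recognised later, when the patient has been dosed and may already have a known response. In a single-arm trial the response proportion and its interval are the main efficacy result, so removing treated patients after the fact changes that result directly.

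Three features make this worse than a drafting detail.

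1. **The rule is one-sided.** A treated patient with prior intensive chemotherapy (exclusion criterion 5) stays in the FAS; a treated patient who failed an inclusion criterion does not. SAP 6.1 defines enrolment by both lists, so the FAS does not match the SAP's own idea of eligibility.
2. **A safeguard loses reach.** Counting an undetermined response as a failure protects the estimate only for patients inside the set. A patient removed from the FAS is not a failure; the patient is simply not counted.
3. **Membership is not governed.** The PPS has a stated timing (immediately before database lock). For the FAS no section states the timing, the decision-maker or the data cut-off.

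**Working it through.** **Who is in which set.** Take four kinds of patient, all with at least one dose:

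| Treated patient | FAS | SES | In planned response rate |
|---|---|---|---|
| Meets all criteria | yes | yes | yes |
| Meets all criteria, response undetermined | yes | yes | yes, as failure |
| Breaks an exclusion criterion only | yes | yes | yes |
| Fails an inclusion criterion, found late | no | yes | no |

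The last row appears in no planned efficacy analysis, because the PPS is drawn from the FAS and the SES is not used for efficacy.

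**Fit with the IWG 2023 endpoint.** Protocol 16.3 (Appendix III b) and SAP 11.2 b, in the row for patients who are not evaluable, ask for all registered patients in the denominator. The endpoint is analysed on the FAS, which leaves out the last row of the table. The two do not agree.

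**Effect on the rate.** The documents print no figure to reproduce here, and the current cohort size is redacted. I assume n = 20 treated in a cohort, with x responders. If k patients are removed, j of them responders, the rate becomes (x − j)/(n − k). The interval is the planned two-sided 90% Clopper-Pearson interval (Protocol 10.8.1):

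- lower limit = 5% quantile of Beta(x, n − x + 1), or 0 if x = 0
- upper limit = 95% quantile of Beta(x + 1, n − x)

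| Case (n = 20 assumed) | Rate | 90% CI |
|---|---|---|
| All treated, 3 responders | 3/20 = 15.0% | 4.2 to 34.4 |
| 3 non-responders removed | 3/17 = 17.6% | 5.0 to 39.6 |
| 1 responder and 2 non-responders removed | 2/17 = 11.8% | 2.1 to 32.6 |
| All treated, 4 responders | 4/20 = 20.0% | 7.1 to 40.1 |
| 3 non-responders removed | 4/17 = 23.5% | 8.5 to 46.1 |
| All treated, 0 responders | 0/20 = 0% | 0 to 13.9 |
| 3 non-responders removed | 0/17 = 0% | 0 to 16.2 |

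With 3 responders, removing 3 non-responders adds 17.6 − 15.0 = 2.6 percentage points, a little under 1 point per patient. The rate rises only if j/k is below x/n; the third row shows it falling when one of the three removed is a responder. With no responders, the situation the SAP document history reports for the interim data, the estimate does not move and only the upper limit rises: 1 − 0.05^(1/20) = 13.9% becomes 1 − 0.05^(1/17) = 16.2%.

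**The case against.** **What stands against a stronger claim.** A reader might infer that the sponsor can remove non-responders from the denominator. The documents do not support that. The sponsor's final say in SAP 7.3 concerns whether a deviation is critical, and deviation status enters the PPS definition, not the FAS definition. For the FAS nobody is named. The rule also takes no account of outcome: it removes an ineligible responder just as it removes an ineligible non-responder.

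A reader might also point to inclusion criterion 3 ("Must be able to adhere to the study visit schedule and other protocol requirements") and argue that a patient who stops attending could be declared ineligible afterwards, or that this criterion and no. 14 can only be judged from later conduct. Neither holds. Protocol 6.3 requires all criteria to be met before inclusion; no. 3 is an ability judged at entry and no. 14 an agreement given at entry. SAP 7.3 treats voluntary early termination as a reason to leave the PPS and not as a protocol deviation, and SAP 7.2 uses drop-outs' data as available. Early leavers stay in the FAS.

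**What limits the size.** Eligibility is checked before dosing and monitored (Protocol 8.1.2, 11.4), so few late inclusion failures should occur; nothing in the documents suggests 3 in 20. All analysis is exploratory (Protocol 10.1), so no type I error is at stake. Exclusions from the sets are listed with reasons (SAP 8.2.1) and response assessments are listed (SAP 8.3), so a careful reader could rebuild an all-treated rate.

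**What this does not answer.** A listing does not restore the headline denominator, and none of these arguments gives a reason for the inclusion-only condition.

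**Conclusion.** The point holds as a defect of definition. As written, the primary efficacy set omits treated patients with a late-found inclusion failure, retains those with an exclusion violation, and has no stated rule for when or on what data membership is settled. OS, PFS, duration of response and best overall response inherit the same restriction. The documents show an opportunity for outcome-aware removal, not an intent, and the direction of any bias cannot be read from them.

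The likely effect is modest: up to 2.6 percentage points for 3 responders in the worst case above, with heavily overlapping intervals, and none on a 0% point estimate. That size rests on an assumed 20 treated patients, an assumed 3 removals, and all of the removals being non-responders. The change is worth making because it removes the question at almost no cost, and because the response rate is the result that readers of a single-arm trial will quote.

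**What to change.** In Protocol 10.2.1 and SAP 4.1.1, define the FAS as all patients who received at least one dose of imetelstat, with no eligibility condition. Handle inclusion and exclusion violations alike, through the PPS only. SAP 7.3 already lists eligibility violations as critical deviations; it would help to say that these are the major deviations named in the PPS definition.

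The FAS and SES then coincide, which SAP 8.8 already covers. The failure rule for undetermined response then reaches every treated patient. The set also comes closer to the IWG 2023 denominator; patients who leave before a first dose count as screening failures under Protocol 6.6 and would still be outside it.

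Cost: one sentence in each document and no new data. The downside is that the reported response rate may be slightly less favourable.

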#### 4.1.2 Per Protocol Set (PPS)

The Per Protocol Set (PPS) will be defined as the subset of patients of the FAS that reached study week [REDACTED] and who have no major protocol deviations as to be determined on a per-subject basis immediately before data base lock.

#### 4.1.3 Safety Evaluation Set (SES)

Safety summaries will be based on the Safety Evaluation Set, which will consist of all patients who received at least one dose of study drug.

### 4.2 Subgroups

To explore separately the efficacy of imetelstat, the analysis of the primary endpoint will be repeated by WHO classification (MDS/AML).

## 5. Interim Analysis

There will be two analyses during this trial:

- An IA at the first stage following assessment of [REDACTED] evaluable patients.
- A final analysis based on the total evaluable [REDACTED] patients if there are [REDACTED] or more responses in the first stage.

The following data will be analysed at the IA:

- Listing of baseline blasts in bone marrow.
- Safety variables (Serious Adverse Events (SAEs), hospitalisations, death due to toxicity and death due to disease).

- Responder (see section 6.2.1, including type of responses, mean blasts in bone marrow (BM cytology assessment) and hematology (automated CBC) baseline value and AML or MDS WHO classification.

## 6. Analysis Variables and Study Endpoints

### 6.1 Disposition, Demographic and Baseline Variables

Disposition	
 
• Screened (defined as signed ICF)
 
• Screening Failure (defined as signed ICF, but terminate the study for any reason before first treatment with IMP)
 
• Enrolled (defined as signed ICF and all inclusion/exclusion criteria fulfilled)
 
• Treated (defined as receiving IMP at least once)
 
• Enrolled in extension treatment phase (from cycle 5 until loss of response)
 
• Completed the study
 
• Discontinuation study 
 
○ Screening Failure
 
○ Withdrawn by subject
 
○ Adverse Event
 
○ Lost of Follow Up
 
○ Protocol deviation
 
○ Pregnancy
 
○ Death
 
○ Physician decision
 
○ Other
 
 
 
• Allocation to analysis sets (FAS, PPS, SES)
 
• WHO Classification (MDS, AML)
 

-------------	---

Demographics	
 
• Age (in years)
 
• Gender (Male/Female)
 
• Race (Black, American Indian or Alaska Native, Asian, Native Hawaiian or other Pacific Islander, White, Not reported, Other)
 

Baseline	
 
• Transfusion history by type of transfusion (RBC, platelets, see 7.7.2 for derivation): 
 
○ Number of units within 16 weeks
 
○ Mean pretransfusion levels (RBC or platelets, in g/dl or mL)
 
○ Rate of units within 16 weeks
 
 
 
• Vital signs 
 
○ Height (in cm)
 
○ Weight (in kg)
 
○ BMI (in kg/m^2)
 
 
 
• ECG 
 
○ PR interval (in msec)
 
○ QRS interval (in msec)
 
○ QT interval (in msec)
 
○ QTcF interval (in msec)
 
○ Heart rate (in beats/min)
 
 
 
• IPSS-R score 
 
○ % blasts in BM (<math>\leq 2</math>, <math>> 2 - < 5</math>, <math>5 - 10</math>, <math>> 10</math>)
 
○ Karyotype (very good, good, intermediate, poor, very poor)
 
○ Hemoglobin (<math>\geq 10</math> g/dl (<math>\geq 6.2</math> mmol/l), <math>8 - < 10</math> g/dl (<math>5 - < 6.2</math> mmol/l), <math>< 8</math> g/dl (<math>< 5</math> mmol/l))
 
○ Platelets (/nl) (<math>\geq 100</math>, <math>50 - < 100</math>, <math>< 50</math>)
 
 
 

	
 
○ Neutrophils (/nl) (<math>\geq 0.8</math>, <math>< 0.8</math>)
 
○ IPSS-R score (very low risk, low risk, intermediate risk, high risk, very high risk)
 
• WHO Classification (MDS, AML) 
 
○ WHO 2016 Classification for MDS
 
○ WHO 2016 Classification for AML
 
 
 

Medical history/ Concomitant medication	
 
• Prior and concomitant medical history (SOC and PT, see section 7.5.2)
 
• MDS/AML related Medical History (Initial WHO 2016 Classification)
 
• Concomitant Procedures
 
• Concomitant medications (for derivation see section 7.5.4)
 
• Prior and concomitant MDS/AML medications
 

